- Prior medications (OTC, prescription) taken for/with weight loss indications: dose, frequency of use, duration of use
- Procedures undertaken for weight loss indications: duration since performed
- Concomitant medications (OTC, prescription) routinely taken by the subject for indications other than weight loss: indication, dose, frequency, duration of use

Diet and Exercise

- Details of the subject's typical daily diet (food and drink consumption), including type of diet followed if applicable (e.g. Keto, Vegetarian, Vegan, Pescetarian, high protein, Atkins, Weight Watchers, etc.)
- Typical exercise patterns type (e.g. running, gym, dance classes, walking, etc.) and frequency.

OUTCOME ASSESSMENT TOOLS

OBJECTIVE ASSESSMENTS

- **Body Weight:** recorded in kilograms (kg)
- **Height:** recorded in inches (in)

- **Body Mass Index (BMI):** calculated as the ratio of weight in kilograms to height in meters squared (m²).
- **Waist and Hips Circumference:** Circumference in inches (ins) for the subject's waist and hips will be measured according to the following protocol at all assessments to ensure consistency across the study:
 - ✓ Hip circumference: measurement will be made such that both hip bones are encircled
 - ✓ Waist circumference: distance in inches from the hip bone to the point at which the circumference of the waist is measured (at the subject's natural waist formation) will be recorded after first measurement to allow for consistent post-treatment measurements

Potential inter-investigator variability will be removed through standardization and training of a sole assessor at each test site.

PRIMARY OUTCOME MEASURE

DIGITAL PHOTOGRAPHS: Subjects will be photographed in a standing position, with relaxed posture. High-resolution digital images will be taken of the subject's abdominal area from the frontal view, and each of the right and left views, at each evaluation visit. Photographs will be acquired using a standardized photography set-up (Google Pixel 8 Pro [50-megapixel], ring light tripod) to ensure consistency, and will be taken in a standardized manner in the same room under the same lighting conditions, with effort made for the images to be taken by the same individual, with the same system settings fixed at the same location, with all subjects situated at the same distance from the lens for each photograph. At each post-baseline visit, the photographer will refer to the baseline photographs to ensure consistency in subject positioning and exposure. Additionally, subjects will be required to wear the same clothing to the test site each time photographic imaging will occur. The same photo imaging control protocols will be employed across all study test sites.

Detailed instructions for the photographs are contained in **Appendix B: Photograph Methodology Instruction Sheet**.

GLOBAL AESTHETIC IMPROVEMENT SCALE: SUBJECT AND PRINCIPAL INVESTIGATOR

The **Global Aesthetic Improvement Scale (GAIS)** is a widely used subjective qualitative assessment tool in clinical trials to evaluate the effectiveness of aesthetic interventions from before to after treatment using a five-point scale ranging from "3: very much improved" to "-1: worse," that enables investigators to provide a standardized evaluation of treatment outcomes. GAIS has demonstrated reliability and clinical relevance and has been validated in multiple studies for use by both the investigator and the subject to assess improvement following aesthetic interventions, including skin laxity.

The Global Aesthetic Improvement Scale Assessment (GAIS) is as follows:

GAIS	Rating	Description
3	Very Much Improved	Optimal cosmetic result
2	Much Improved	Marked improvement in appearance from the initial condition, but not completely optimal
1	Improved	Obvious improvement in appearance from initial condition, but a re-treatment is indicated
0	No Change	The appearance is essentially the same as the original condition
-1	Worse	The appearance is worse than the original condition

SUBJECT SATISFACTION WITH STUDY OUTCOME: The subject is asked to rate how satisfied he or she is with any change in the appearance of the skin laxity of the abdomen region following completion of the laser administration procedure with the Erchonia® GVS by using the 5-point Likert scale below to respond to the following question: “Overall, how satisfied or dissatisfied are you with any change in the appearance of the skin of your abdomen following the study procedures with the study laser device?”

- Very Satisfied
- Somewhat Satisfied
- Neither Satisfied nor Dissatisfied
- Not Very Satisfied
- Not at All Satisfied

SUBJECT-REPORTED PERCEPTION OF SKIN TIGHTNESS: Following the completion of the laser treatment with the Erchonia® GVS device, subjects will be asked to assess perceived changes in abdominal skin tightness. Using the 5-point Likert scale provided below, subjects will respond to the question: “Overall, compared to before your treatment with the study device, how much tighter does the skin on your abdomen feel now?”

- A lot tighter
- A little tighter
- No change
- A little less tight,
- A lot less tight.

STUDY PROCEDURES

PRE-TREATMENT ACTIVITIES

The pre-treatment activities will be conducted at the test site prior to administration of the initial study treatment with the Erchonia® GVS.

SIGNING OF INFORMED CONSENT FORM

The investigator will commence by presenting and reviewing in detail the items in the informed consent form with the individual and answer any questions. To proceed, the individual must willingly sign the informed consent form.

ASSIGNMENT OF SUBJECT ID

The subject will be assigned a unique subject identification number based upon the test site and his or her order of entry into the study.

Additional information about the informed consent and subject ID number assignment is contained in a later section of the protocol titled, "SAFETY AND CONFIDENTIALITY ISSUES."

STUDY QUALIFICATION EVALUATION: INCLUSION/EXCLUSION CRITERIA

INCLUSION CRITERIA

To be eligible for participation in this study, a subject must satisfy each of the following.

- Subject has signed a written informed consent form.
- Male or female 22 to 70 years of age, inclusive.
- Desire to undergo treatment for skin laxity of the abdomen.
- Subject's score on the skin laxity scale for skin on the abdomen is 1 (mild) or 2 (moderate).
- Subject agrees to maintain his/her weight (i.e., within 5%) by not making any major changes in diet, exercise or medication routine during the course of the study.
- Subject agrees to refrain from taking any medication(s) or supplements(s), whether prescription or OTC, or undergo any procedures indicated for weight loss, or for fat reduction or improving the appearance of the skin in the abdominal area (e.g. liposuction, ultrasound therapy) for the duration of participation in the clinical study.
- Willing to have research photos taken of treatment areas.
- Understands, and is able and willing to comply with all study visits, treatments and evaluations schedules and requirements.
- Females are at least 9 months post-partum.
- Females are post-menopausal, surgically sterilized, or using a medically accepted form of birth control for at least 3 months prior to the study and agree to continue to do so for the duration of study participation.

EXCLUSION CRITERIA

A subject who satisfies any of the following criteria will be excluded from study participation:

- Skin laxity resulting from genetic disorders, including but not limited to Ehlers-Danlos Syndrome.
- History of undergoing a fat reduction procedure (e.g., liposuction, bariatric surgery, abdominoplasty).
- Botulinum toxin or other aesthetic drug injections within the abdomen area within the past 6 months.

- History of any major prior surgery in the abdominal area
- Implanted medical prostheses (such as clips, pins or plates) in or adjacent to the area of intended treatment.
- Active implanted device such as a pacemaker, defibrillator, or drug delivery system.
- Any clinical and significant dermatological skin condition(s) in the intended abdominal treatment area, such as skin infections or rashes, extensive scarring, psoriasis, etc..
- Tattoo or former tattoo at the treatment area.
- Current moderate to heavy tobacco use, defined as smoking 10 or more cigarettes per day (or equivalent use of other nicotine-containing products such as cigars, pipes, chewing tobacco, or e-cigarettes) within the past 6 months
- History of chronic drug or alcohol abuse.
- Pregnant or intending to become pregnant in the next 6 months.
- Currently enrolled in a clinical study of an unapproved investigational drug or device.

PRE-TREATMENT EVALUATIONS

The following pre-treatment measures will be recorded prior to commencement of the treatment administration phase (prior to treatment administration #1).

BASELINE VARIABLES

- Subject Demographics
- Medications and Procedures
- Diet and Exercise

PRE-TREATMENT OUTCOME ASSESSMENTS

- Body Mass Index (BMI)
 - Height (in)
 - Weight (kg)
- Circumference measurements: waist and hips
- Digital Photographs

TREATMENT ADMINISTRATION PHASE

TREATMENT ADMINISTRATION PROTOCOL

- The treatment administration phase of the study may commence on the same day as the pre-treatment measurements are recorded.
- The treatment administration phase will extend over four consecutive weeks.
- Each subject will receive eight total treatment administrations with the Erchonia® GVS across the consecutive four-week treatment administration phase; two treatment per week; each one at least two days apart.
- Each treatment will take place at the investigator's test site.
- The treatment administration protocol for each session is as follows:
 1. The subject enters the treatment administration room and lays comfortably on a treatment table.
 2. The subject is correctly fitted with the safety glasses.
 3. The center of the Erchonia GVS treatment head is positioned approximately 4 inches above the subject's abdomen. The GVS treatment head is aligned so that one set of the three central laser diodes is positioned over the left side of the abdomen, while the other set of three central diodes is positioned over the right side of the abdomen.
 4. The two adjustable outer arms of the Erchonia GVS are then positioned over the left and

- right flanks, respectively, at a distance of approximately 4 inches.
5. The Erchonia® GVS is activated for 30 minutes. Each laser beam will create a spiraling circle pattern that is totally random and independent from the others. These patterns overlap each other to guarantee total coverage within the target area (abdomen).
 6. The Erchonia® GVS treatment will run 30 continuous minutes and will stop once treatment time is at 0:00. Once the “Time Remaining” display reaches 0:00 the treatment is complete, and the laser lights and the laser indicator light will turn off.
 7. After the Erchonia® GVS is turned off, the subject removes the safety glasses and leaves the treatment administration room.

TREATMENT ADMINISTRATION RECORD

Following the completion of each treatment with the GVS laser, the investigator will record the following:

- Number of treatment administration
- Date
- Investigator signature
- Adverse event (if applicable).

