Low-level light therapy (LLLT) is a fast-growing technology, proven and FDA market cleared for non-invasive body contouring, including the area of the abdomen. It has also been proven effective in improving skin laxity. As explained in detail above, the skin responds well to LLLT wavelengths where the laser photons are absorbed by mitochondrial chromophores in cells leading to an increase in adenosine triphosphate (ATP) release thus improving blood flow and reactive oxygen species.

It therefore follows that the Erchonia GVS is ideally suited to effecting a statistically significant and clinically meaningful aesthetic improvement in the appearance of skin laxity of the abdomen of males and females following completion of administration of the full treatment protocol, thus providing a viable and desirable option for the ever-growing patient population seeking cost-effective non-invasive treatment alternatives with minimal to no downtime for improvement in the appearance of abdominal skin laxity.

STUDY DESIGN AND METHODOLOGY

STUDY DESIGN

This clinical study is a prospective single-arm design with post-hoc analysis of study primary efficacy by independent blinded evaluators intended to evaluate the efficacy of the Erchonia® GVS Laser in providing noninvasive improvement in the appearance of skin laxity of the abdomen region.

SUBJECT GROUP

There is a single active treatment only subject group in this study.

RANDOMIZATION

As all enrolled subjects in this study will knowingly receive the active study treatment with the Erchonia® GVS, randomization to treatment group is not applicable.

STUDY BLINDING

As all enrolled subjects in this study will knowingly receive the active procedure administration with the Erchonia® GVS, neither the subjects nor the study investigators will be blinded.

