5. Subject-Reported perception of Skin Tightness at 4 and 12 weeks post-final treatment.

Subject-Reported perception of Skin Tightness outcome ratings recorded at each of 4 and 12 weeks post-final treatment will be assessed and compared.

COVARIATE/SUBGROUP ANALYSIS

The impact of the following potential covariates on the primary study efficacy outcome may be evaluated, as indicated:

- Age
- Gender
- Ethnicity
- Race
- Baseline height (m)
- Baseline body weight (kg)
- Baseline BMI (kg/m^2)
- Baseline waist circumference measurement (in)
- Baseline hips circumference measurement (in)

ADDITIONAL CONSIDERATIONS

Depending on the variations identified, a discussion on the potential impact of variability in subject reported use of medications and procedures, and diet and exercise patterns at baseline assessment may occur.

SAFETY ANALYSES

Safety will be assessed by evaluating observed and/or reported adverse events.

ADVERSE EVENTS

At each evaluation and measurement point throughout the clinical study, and at any other time throughout the duration of the clinical trial that is necessary, all potential adverse events reported by a subject or observed by an investigator will be recorded on the case report form, and subsequently evaluated by the investigator for its relation to the study procedure and whether any corrective action needs to be taken. All potential adverse events recorded will be appropriately reported to the governing IRB, as applicable.

It is unlikely and not expected that any adverse events will result from implementation of this clinical study protocol. Prior clinical trials using low level laser light, including the prior Erchonia clinical study evaluating the Erchonia green and violet laser combination, have not typically yielded any adverse events or reactions. However, potential adverse events that may feasibly occur from application of the Erchonia® GVS include, but are not necessarily limited to skin irritation, discoloring, rash, indentations, and infection.

ADVERSE EVENTS DEFINITION

An adverse event means any untoward medical occurrence associated with the use of an intervention in humans, whether or not considered intervention-related (21 CFR 312.32 (a)).

SERIOUS ADVERSE EVENTS (SAE) DEFINITION

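### The stem of the skin-tightness question names only improvement, which may tilt an unblinded, uncontrolled supportive self-report towards benefit

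*Combined protocol and SAP*

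**What the plan says.** The item is defined in the combined protocol and SAP under Subject-Reported Perception of Skin Tightness, within the outcome assessment tools. Its purpose is stated neutrally: "subjects will be asked to assess perceived changes in abdominal skin tightness". The question put to the subject is then "how much tighter does the skin on your abdomen feel now", with the period before treatment as the reference. The answer is given on a five-point scale with two grades of tighter, a neutral midpoint and two grades of less tight, the last being "A lot less tight".

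The item directly above it, Subject Satisfaction with Study Outcome, asks "Overall, how satisfied or dissatisfied are you with any change in the appearance of the skin of your abdomen".

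On design, Subject Group states "There is a single active treatment only subject group in this study", and Study Blinding states that "neither the subjects nor the study investigators will be blinded". Both questions are scheduled at the end-of-treatment visit and at the 12-week visit. Neither appears among the pre-treatment assessments.

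Secondary Efficacy Evaluations, item 5, says that "Subject-Reported perception of Skin Tightness outcome ratings recorded at each of 4 and 12 weeks post-final treatment" will be assessed and compared. (The label for the earlier visit differs between this section and Study Procedures; that does not bear on the present point.) The opening paragraph of the same section describes all five secondary evaluations as supporting the primary. It adds that the sponsor plans no claim from them, that they are reported descriptively, and that change is not analysed statistically.

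**The concern.** A question that asks how much tighter the skin feels takes tightening as given and asks only for its degree. A subject who feels no change, or a loosening, has to answer against the question. The stem therefore fits neither the purpose stated for the item nor its own response scale.

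This matters more here than it would in a blinded, controlled trial. All subjects know they had active treatment, and under the inclusion criteria all of them wanted treatment for abdominal laxity, so expectation already favours a good report. What is at stake is the credibility of one supportive percentage: the share of subjects who say their skin is tighter. The study is meant to support a 510(k) submission, and a reader of that submission could fairly ask how much of the percentage comes from the wording.

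**Working it through.** The plan attaches no sample size, threshold or expected distribution to this item, so there is no figure to reproduce and no formula to apply. The check is a comparison of the texts.

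1. **Purpose against stem.** The purpose is perceived change in either direction. The stem, "how much tighter does the skin on your abdomen feel now", covers one direction. They do not match.

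2. **Stem against options.** The options are 2 favourable, 1 neutral and 2 unfavourable, which is symmetric. The defect is in the stem alone.

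3. **Stem against the neighbouring item.** "how satisfied or dissatisfied are you with any change in the appearance of the skin of your abdomen" names both directions and does not presume that anything changed. The protocol thus already uses a balanced stem for the same subjects at the same visits. The comparison holds for the stems only: the two lowest satisfaction answers are worded as degrees of not being satisfied, and the word dissatisfied appears only in the midpoint.

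4. **Could the analysis reveal or remove a tilt?**
   - Between arms: no, because there is one arm.
   - Through blinding: no, because subjects are unblinded.
   - Against baseline: no. Pre-Treatment Outcome Assessments lists BMI with height and weight, waist and hip circumference, and photographs. The Skin Laxity Scale is used for qualification and is not a subject rating of tightness.
   - Between the two visits: no. The same stem is used at both, so a tilt common to both would not show in the comparison.

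5. **Reach.** The primary endpoint rests on three independent evaluators who sort photographs without knowing which came first. No subject answer enters it.

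6. **Scale of the reported percentage.** With all 35 enrolled subjects answering, one subject is 1/35 = 2.9 percentage points; with the 30 in the sample size calculation, 1/30 = 3.3 points. This converts subjects into points. It does not estimate bias, because the documents give nothing from which to say how many subjects, if any, would answer differently.

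**The case against.** The strongest case against the point is that it is close to an editorial preference. No decision rests on the item: it is descriptive, no claim is planned from it, and the success criterion lies elsewhere. The subject answers from a displayed scale with an explicit neutral option and two worsening options, which is more symmetric than the satisfaction scale. Nothing in the documents shows that the stem changes answers when such options are in view. The larger weakness, an unblinded self-report without a control, would remain after any rewording. The subject's own GAIS rating also gives a separate report of direction.

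Most of this stands, and it sets the severity. It does not justify a stem that conflicts with the item's stated purpose. With no statistical analysis planned, the value of a descriptive percentage depends largely on how the question is asked. The subject GAIS is not a neutral check either: it rates appearance rather than how the skin feels, and it offers three grades of improvement against one of worsening.

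Three stronger readings are tempting, and the documents support none of them:

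- A reader might attach a number, for example that the stem moves 5% to 15% of subjects from no change to slightly tighter: 0.05 × 35 = 1.75 and 0.15 × 35 = 5.25, or about 2 to 5 subjects (6 to 14 points). That range has no source in the documents and, by excluding zero, assumes the effect in dispute.
- A reader might infer that rewording gives nothing up because no validation is claimed for the item. The protocol claims validation for the GAIS and is silent on where this item came from. Silence does not show that the wording is free to change, only that the documents identify no established wording that would be lost.
- A reader might infer that the efficacy conclusion is compromised. It is not, because the primary endpoint uses no subject report.

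**Conclusion.** The point holds as a minor one. The stem names only the favourable direction, against the item's own purpose and response scale, and this may tilt a supportive self-report towards benefit. The lack of a control, of blinding and of a baseline rating means that such a tilt could be neither detected nor removed.

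The direction is a reasoned inference from the wording, not a finding shown in the documents. The size is unknown. The conclusion also assumes that the case report form, which was not available to read, carries the same stem as the protocol text.

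**What to change.** Keep the five response options and the opening clause that sets the comparison with the time before treatment. Replace the rest of the stem with a neutral, graded question, for example: *how would you describe any change in how tight your abdominal skin feels now?* The question should stay graded. A three-way stem (tighter, less tight or the same) would not fit answers that distinguish a lot from a little.

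Make the change in the protocol and on the case report form together. The cost is one line in each, submitted as an amendment for IRB approval before implementation, with re-consent where applicable, as Protocol Amendments requires. Sample size, endpoints and analysis stay as they are.

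The documents do not state whether enrolment has begun. If any subjects have already answered the item with the present stem, report the results for the two stems separately.

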The Erchonia® GVS is classified by the IEC as a Class 2 laser device. This designation represents a current standard for use in order to ensure the safety of the patient. A Class 2 laser is determined to have a chronic viewing hazard. Pointing the laser beam directly into the eye and maintaining it there for an extended period of time could prove to be damaging. To ensure there is no possible instance of residual effect, we have included a pair of specialty glasses for use by the patient during treatment. 100-10-110 is an ultra-light-weight comfortable frame with a double coated scratch-resistant polycarbonate laser filter. The fit-over-prescription style frame offers universal fit with wide field of view. Lens has superior optical clarity with virtually no distortion to reduce eye fatigue. It is ideal for use in most laser applications and comfortable for long periods of wear. These safety glasses sufficiently and effectively block the laser light spectrum at OD 6+ @ 190-532 nm, OD 6+ @ 10,000-11,000 nm.

Height: 63.8 mm
Width: 155.3 mm
Length: 140-160 mm

WARNING- The patient should always be correctly fitted with the safety glasses provided before turning on the laser and doing any treatment.

STUDY BACKGROUND AND RATIONALE

STUDY INDICATION: ABDOMINAL SKIN LAXITY

Definition of Abdominal Skin Laxity

Skin laxity is defined as the acquired loose, relaxed state of the skin that develops from skin extensibility (stretch) and decreased skin recoil (return to original state after stretch). Skin laxity of the abdomen is visible as the appearance of loose and sagging skin on the stomach that results from a loss of elasticity.

Causes of Abdominal Skin Laxity

Intrinsic and extrinsic aging causes specific cutaneous changes, such as epidermal thinning, loss of collagen, degradation of elastin, and redistribution of subcutaneous fat, that all lead to significant abdominal skin laxity. However, there are several additional factors that can exacerbate the appearance and accelerate the onset of abdominal skin laxity include advanced age, key amongst which are the following:

- *Weight Loss*: Significant, especially rapid, weight loss, can leave skin stretched and unable to contract back to its original shape, resulting in loose skin.
- *Pregnancy*: Pregnancy stretches the skin of the abdomen, and postpartum, the skin may not fully return to its original state, leading to sagging.

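### No weight-stability requirement before baseline for non-surgical weight loss, so in a single-arm photograph trial change already under way at entry can count toward the responder rate

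*Combined protocol and SAP*

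**What the plan says.** All of this comes from the combined protocol and SAP.

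- **Causes of Abdominal Skin Laxity** lists weight loss and pregnancy side by side. On weight loss: "Significant, especially rapid, weight loss, can leave skin stretched and unable to contract back to its original shape, resulting in loose skin". On pregnancy: "postpartum, the skin may not fully return to its original state, leading to sagging".
- **Inclusion Criteria**, pregnancy: "Females are at least 9 months post-partum". No reason is given for the 9 months.
- **Inclusion Criteria**, weight: "Subject agrees to maintain his/her weight (i.e., within 5%) by not making any major changes in diet, exercise or medication routine", for the course of the study. A separate criterion has the subject forgo weight-loss drugs, supplements and procedures while participating. Neither reaches back before entry.
- **Exclusion Criteria**: "History of undergoing a fat reduction procedure (e.g., liposuction, bariatric surgery, abdominoplasty"), with no time limit. Major prior abdominal surgery is also excluded.
- **Baseline Variables, Medications and Procedures**: "Prior medications (OTC, prescription) taken for/with weight loss indications: dose, frequency of use, duration of use". For weight-loss procedures the time since performance is also listed. For prior drugs no stop date is listed, and prior body weight is not a listed variable.
- **Subject Group**: "There is a single active treatment only subject group in this study".
- **Primary Efficacy Outcome**: a responder is a subject whose baseline and 12-week photographs are put in the right order by at least 2 of 3 blinded evaluators. Success is a responder rate of at least 80%.
- **Covariate/Subgroup Analysis** does not list weight-loss history. **Additional Considerations** allows, but does not require, a discussion of baseline differences in medication, procedures, diet and exercise.

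**The concern.** The endpoint records whether evaluators can tell the later photograph from the earlier one. It does not record why they differ. With no control arm, entry criteria are one of the few protections against change that began before treatment.

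Two kinds of subject pass the present criteria:

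1. A subject still losing weight on an unchanged diet and exercise routine. Keeping to the routine satisfies the wording about major changes, and a loss of up to 5% on study stays within the limit. The abdomen may look different for that reason alone.
2. A subject who completed a non-surgical loss shortly before baseline and is weight-stable from then on. Any skin change continuing after that loss would fall inside the roughly 16 weeks between the two photographs (4 weeks of treatment plus 12 of follow-up).

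The on-study weight and circumference measurements can show the first. They need not show the second, because the cause precedes baseline. Without a stop date or a prior weight among the listed variables, the second group could not be identified reliably afterwards, even for a sensitivity analysis.

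**Working it through.** **The criteria side by side.**

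| Cause or exposure | Period before entry | Period on study |
|---|---|---|
| Pregnancy | at least 9 months post-partum | contraception, sterilisation or menopause |
| Surgical or procedural fat loss | any history excluded | not allowed |
| Weight loss by diet or exercise | none | within 5%, no major change of routine |
| Weight loss by medication | none (recorded only) | not allowed |

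The last two rows are the gap.

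**The plan's own sample-size figure.** Rationale for Sample Size gives N = 30, exact binomial test, alpha 0.025, power 90%, P0 = 0.80, P = 0.50.

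- Lower tail with the printed proportions: reject at X ≤ 18, alpha 0.0095, power 0.8998.
- Proportions swapped (0.50 against 0.80): reject at X ≥ 21, alpha 0.0214, power 0.939.
- Printed direction (alternative P > P0): reject at X ≥ 29, power about 3 × 10⁻⁸.

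So N is reproduced only if the direction or the labels are reversed. That needs its own correction and does not bear on eligibility. Enrolment of 35 matches 30 × 1.15 = 34.5, rounded up.

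**Effect on the success rule.** The primary population is all 35 enrolled, and 0.80 × 35 = 28, so success means at least 28 responders.

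Assumed inputs, none of them in the documents:

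- k = number of subjects whose appearance changes for reasons preceding baseline: 0, 3 or 7.
- Responder probability for those subjects: 0.95.
- Responder probability b for the rest: 0.50 to 0.75. The value 0.50 is pure guessing by three evaluators: 3 × 0.5² × 0.5 + 0.5³ = 0.375 + 0.125 = 0.50.

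Formulas: expected rate = [0.95k + b(35 − k)] / 35. Chance of success = P(A + B ≥ 28), with A ~ Binomial(k, 0.95) and B ~ Binomial(35 − k, b) independent.

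Example at b = 0.70, k = 7: (6.65 + 19.60) / 35 = 26.25 / 35 = 0.750. At k = 3: (2.85 + 22.40) / 35 = 0.721.

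| Base rate b | P(≥28), k = 0 | k = 3 | k = 7 |
|---|---|---|---|
| 0.50 | 0.0003 | 0.001 | 0.005 |
| 0.60 | 0.010 | 0.023 | 0.060 |
| 0.70 | 0.13 | 0.20 | 0.32 |
| 0.75 | 0.32 | 0.41 | 0.54 |

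**Stress test, inert device.** Suppose a share f of subjects is always identified and the rest are guessed, giving a common rate f + 0.5(1 − f). With n = 35, P(≥28) is 0.0003, 0.010, 0.042, 0.13 and 0.32 at f = 0, 0.2, 0.3, 0.4 and 0.5. Drift alone needs a large affected share before success becomes likely.

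**The case against.** The strongest objection concerns mechanism. A reader might infer that the 9 months post-partum is there to ensure settled tissue, and that subjects with recent weight loss have skin still retracting that will improve without the device. The documents state neither. They give no reason for the 9 months, and the background says weight loss can leave skin unable to contract back, which describes lasting laxity rather than recovery. This stands: continuing recoil is an inference. It does not dispose of the point, because a subject still losing weight within the 5% limit needs no such mechanism.

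A reader might also infer that anyone with a large recent loss meets every criterion. That goes too far. Bariatric surgery, liposuction and abdominoplasty are excluded for life, weight-loss drugs must not be taken on study, and laxity must be mild or moderate. A subject losing weight on a drug would have to stop it, which sits awkwardly with the undertaking not to change medication routine. What remains open is non-surgical loss that is recent, or that continues on an unchanged diet and exercise routine.

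It can further be said that the missing control arm is the real weakness and that the arithmetic rests on chosen inputs. Both are true. A single-arm design, however, makes entry criteria matter more, and the range of base rates shows where the effect is small. Finally, the case report forms are not among the documents reviewed, so the remarks on stop date and prior weight concern only the variables listed in the protocol.

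**Conclusion.** The gap holds in its narrower form. The plan has no pre-baseline weight-stability requirement for loss by diet, exercise or medication, and the single-arm photograph endpoint would count any resulting visible change as response. The direction of bias is toward success wherever the change makes the later photograph easier to pick out.

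The size is unknown, because neither the share of such subjects nor the visibility of the change is given. Under the assumptions above, the risk is modest and concentrated near the threshold: at base rates of 70% to 75% the chance of success rises by about 6 to 22 percentage points (0.13 to 0.20-0.32, and 0.32 to 0.41-0.54). At a 50% base it stays at or below 0.005. The documents therefore do not support reading this as a route by which an inert device would probably succeed. It is worth correcting before enrolment because the correction is cheap and weight history is hard to recover later.

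**What to change.** 1. Add an inclusion criterion that body weight has been stable within the plan's own 5% over a stated period before baseline, by record or subject report. The plan uses no look-back figure for weight, so the sponsor should set and justify the length.
2. Add to the listed baseline variables the stop date of any prior weight-loss medication and the body weight at the start of that look-back period.
3. If any subject with recent weight loss is enrolled, report the primary responder rate with those subjects excluded, as a prespecified sensitivity analysis.

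The cost is one criterion, two data fields and one extra table. Some subjects with recent weight loss would be deferred, so recruitment would be modestly slower. Planned N does not change. If the sponsor prefers to keep entry open, items 2 and 3 alone would at least let the influence of these subjects be examined.
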